Number of Subjects: 130 patients per group for a total of 390 patients		
Number of centres: around 100 centres		
Diagnosis and Main Criteria for Inclusion: Inclusion criteria: 
 1. Male or non-pregnant, non-breast feeding female; 2. Aged ≥ 18 years; 3. Patients with 
 – advanced HCC (BCLC-C according to BCLC staging classification) having progressed under Sorafenib therapy or intolerant to Sorafenib, or – intermediate HCC (BCLC-B) non eligible or non responders to transarterial chemoembolization (TACE), and having progressed under or intolerant to Sorafenib therapy; 4. Patients with porta hepatis lymph nodes, extrahepatic metastases, or portal/suprahepatic vein thrombosis without extension in inferior/superior vena cava, are eligible; 5. HCC diagnosed according to the AASLD and/or EASL criteria: 		

NAME OF COMPANY: Onxeo (formerly known as BioAlliance Pharma)	NAME OF FINISHED PRODUCT: Doxorubicin Transdrug™ 10 mg	NAME OF ACTIVE INGREDIENT: Doxorubicin

 – Radiological Criteria applicable in cirrhotic liver: 
 – Nodule \geq 10 mm: one imaging technique among MRI and CT-scan showing typical appearances for HCC defined as arterial enhancement and rapid washout in portal venous or delayed phase; – If appearance not typical for HCC on initial imaging: second contrast enhanced study (CT or MRI) showing typical appearances for HCC defined as arterial enhancement and rapid wash-out in portal venous or delayed phase; – And/Or cyto-histology criteria (e.g. in case of atypical lesions for HCC at imaging, absence of cirrhosis); 
6. Without cirrhosis or with a non decompensated cirrhosis (Child-Pugh score from A5 to B7 included);
 
7. ECOG Performance Status 0 or 1;
 
8. Adequate laboratory tests, in particular with:
 
 – Platelets \geq 50,000/mm³ – Neutrophil count \geq 1000 /mm³ – Hemoglobin \geq 10g/dL – Serum transaminases < 5 ULN (NCI/CTC grades 0, 1, or 2) – Alkaline phosphatases < 5 ULN (NCI/CTC grades 0, 1, or 2) – Serum bilirubin < 35 μM/L (or 2.0 mg/dL); 
9. Signed and dated written informed consent form.
		

Exclusion criteria: Patients with any of the following criteria must not be included
		

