3 TRIAL DESIGN

This is a multicentre, open-label, randomised, comparative, 3 arms (DT 20 mg/m², DT 30 mg/m², Best Standard of Care) study in patients suffering from hepatocellular carcinoma.

The study will be carried out at multiple hepatology or oncology centres that manage patients with HCC with or without cirrhosis. Approximately 100 centres will be involved in the trial.

Based on the survival data obtained in the phase II clinical trial, it has been calculated that 390 patients have to be included to adequately compare the efficacy of DT 20 mg/m² and DT 30 mg/m² to that of BSC.

A safety evaluation will be carried out on a regular basis at least twice a year by the Data Safety Monitoring Board (DSMB) and every 75 patients (around 25 patients/group) whichever comes first.

Patients who meet the inclusion/exclusion criteria will be randomised according to a 1:1:1 ratio to receive either DT 20 mg/m², DT 30 mg/m², or BSC. Only those patients whose survival expectations is longer than 2 months and could receive more than 1 DT infusion will be enrolled.

The study duration for each patient includes a screening period of 28 +/- 2 days maximum before baseline visit (D0 Cycle 1). The patient will then be randomised to receive either DT 20 mg/m² or DT 30 mg/m² as protracted IV infusion over 6 hours once every 4 weeks or BSC.

Patients will receive study therapy until unequivocal tumour progression (assessed by the investigator) or occurrence of unacceptable toxicity.

All patients will be evaluated by CT scan or MRI every 2 months for tumour assessments.

After study therapy discontinuation, an end of study visit will be performed 1 month +/- 7 days after the last DT infusion or last BSC treatment.

Then, a follow up of all patients (including those who withdrew prematurely from the study) will be maintained every 3 months until death. The following information will be recorded:

- Survival (patient alive or deceased)
- Date of progression (in the case of withdrawal for other reason than progression during the study treatment period)
- Administration of any other anti-cancer treatment.

The follow-up period is defined as “until 2 years after Last Patient In”.

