9.1.3 General conventions

Descriptive statistics for parameters of interest will be provided by treatment group (pooled DT groups, DT 20 mg/m² alone, DT 30 mg/m² alone and BSC control group) and overall.

The baseline value will be defined as the last available value prior to first DT infusion for patients in tested dose groups or prior to first BSC administration for patients in BSC.

The type I (α) error will to be 5% (two-sided) for all analyses.

From a statistical point of view, this study will not be comparative between the two doses of DT. So comparison of confidence intervals between each DT group versus BSC will be exploratory in order to define the benefit-risk ratio for each dose (see 9.6).

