9.6 Determination of the optimal dose of DT

The statistical analyses comparing the experimental group (pooled DT 20mg/m² and 30mg/m² groups) versus BSC will also be conducted in the DT 20mg/m² group alone vs BSC and DT 30mg/m² group alone vs BSC in the ITT population.

Baseline demographic characteristics, exposure, efficacy, safety and adjustment for covariates (as described in Sections 9.3, 9.4 and 9.5 of the protocol) will be compared for each DT group versus BSC (as exploratory analysis).

The selection of the optimal DT dose will be based on the benefit/risk ratio of each dose of DT, taking into account:

- **Benefit/Efficacy:** The optimal dose of DT in term of efficacy will be the one which is associated with the best survival in comparison with the BSC group.

This will be assessed through the measure of OS and tested by the unstratified log-rank test.

The optimal dose for efficacy will be identified if one out of the 2 exploratory unstratified log-rank tests between the DT 30 mg/m² versus BSC or DT 20 mg/m² group versus BSC is statistically significant or if a clinically relevant difference is observed in favour of one DT group versus BSC (i.e. unstratified log-rank tests between the DT 30 mg/m² versus BSC or DT 20 mg/m² group versus BSC less than 15%).

If there is no difference between the DT 30mg/m² versus BSC and DT 20mg/m² group versus BSC (i.e. unstratified log-rank tests between the DT 30 mg/m² versus BSC or DT 20 mg/m² group versus BSC more than 15%), it will be concluded that DT 20 mg/m² and DT 30 mg/m² are similar in term of efficacy.

- **Risk/Safety:** The optimal dose of DT in term of safety will be the one which is associated with the lowest incidence of treatment discontinuations due to adverse drug reactions and the lowest incidence of deaths due to adverse drug reactions.

Difference between the two doses of DT (DT 30 mg/m² versus DT 20 mg/m²) will be explored via two-sided Fisher exact tests on the incidence of treatment discontinuations and on the incidence of death due to adverse drug reactions.

If at least one exploratory Fisher test leads to conclude to a statistically significant difference between the DT 30 mg/m² group and the DT 20 mg/m² group, or if a clinically

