relevant difference is observed between groups (absolute difference of more than 5%), the optimal dose of DT for safety will be the one which is associated with the lowest incidence of study treatment interruptions or deaths due to adverse drug reactions. If there is no difference between the dose groups for these safety criteria, it will be concluded that DT 20 mg/m² and DT 30 mg/m² are similar in term of safety.

In summary, the optimal DT dose will be the dose of DT associated with the best OS (if any). If OS is similar between the 2 doses of DT, the optimal DT dose will be the one associated with the best tolerance. If OS and safety are found to be comparable between doses, then the lowest dose (20mg/m²) will be selected.

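### Section 9.6 would report the two DT doses as similar in safety from non-significant tests and small observed gaps, with no confidence bound behind the claim

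*Combined protocol and SAP*

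**What the plan says.** The safety part of section 9.6 sets two criteria for comparing DT 30 with DT 20. The difference "will be explored via two-sided Fisher exact tests on the incidence of treatment discontinuations and on the incidence of death due to adverse drug reactions".

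Two triggers can declare a difference:
- The first is a test: "If at least one exploratory Fisher test leads to conclude to a statistically significant difference".
- The second is an observed gap: a clinically "relevant difference is observed between groups (absolute difference of more than 5" per cent.

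If either trigger fires, the dose with the lower incidence is the better one for safety. If there is no difference on these criteria, "it will be concluded that DT 20 mg/m² and DT 30 mg/m² are similar in term of safety". The same 5-point cut-off serves both criteria. No confidence interval, margin or error rate is attached.

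The summary at the end of section 9.6 uses overall survival (OS) first, tolerance only if OS is similar, and the lower dose if both are comparable. Section 9.1.3 sets the level ("The type I (α) error will to be 5% (two-sided) for all analyses") and says that the study is not comparative between the two doses.

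**The concern.** A non-significant test shows that a difference was not detected. It does not show that the difference is small. The 5 points do not repair this, because they are compared with the point estimate and no confidence bound has to fall inside them. Five points is also a large absolute difference for fatal drug reactions, yet it is the cut-off used for discontinuations too.

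Section 9.8 reasons differently. There, no events in 25 patients is explicitly said to leave open a true incidence above 11.29%. Section 9.6 drops that logic for the comparison between doses.

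The stake is a positive statement of similar safety for a drug with known fatal lung toxicity. Section 7.6.1 reports 5 ARDS cases, two of them fatal, by the earlier route, and names dose and infusion rate as drivers of toxicity.

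**Working it through.** **Inputs from the documents.** Synopsis: "130 patients per group for a total of 390 patients". Section 3: "randomised according to a 1:1:1 ratio", so 130 v 130 for the two doses. Alpha is 0.05 two-sided (section 9.1.3). The triggers are those of section 9.6.

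**Assumed.** The documents give no rates of fatal reactions or discontinuations for the 6-hour IV regimen, so ranges are shown. The size of the safety population is not stated; 117 (130 × 0.9) is a sensitivity value.

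**The plan's own figures.** Section 9.6 states no operating characteristic. Nearby figures do reproduce: 348/0.9 = 386.7, so 387 against the stated 390. The section 9.8 bound for 0/25 is 1 − 0.05^(1/25) = 11.29%, as printed.

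**Step 1: what triggers a flag.** 6/130 = 4.6% and 7/130 = 5.4%, so the gap trigger needs 7 patients. Among splits with a gap of 6 or fewer, Fisher is significant only for 0 v 6 (p = 0.029) and its mirror images. Each of these splits in deaths has a gap of 4.6 points and raises no flag:

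| Deaths | Fisher p | 95% CI for difference (Newcombe), points |
|---|---|---|
| 1 v 7 | 0.066 | +0.2 to +10.0 |
| 2 v 8 | 0.103 | −0.3 to +10.2 |
| 6 v 12 | 0.221 | −1.8 to +11.3 |

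**Step 2: chance of no flag on deaths.** Let S be the set of count pairs (a, b) with Fisher p ≥ 0.05 and |a − b|/130 ≤ 0.05. For true rates p and q,

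P(no flag) = Σ over (a, b) in S of Bin(a; 130, p) × Bin(b; 130, q).

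| True rates | Deaths alone | Both criteria* |
|---|---|---|
| 1% v 2% | 98.5% | 81% |
| 2% v 4% | 91% | 75% |
| 3% v 6% | 78% | 64% |
| 4% v 8% | 64% | 52% |
| 5% v 10% | 50% | 41% |

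*Multiplied by 0.822, the chance of no flag on discontinuations if these are 10% at both doses and independent of deaths; for 2% v 4%, 0.910 × 0.822 = 0.748.

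Triplings are caught more often: 2% v 6% is unflagged on deaths in 66% of trials, and 3% v 9% in 37%. With 117 per dose, 2% v 4% is unflagged in 89% and 5% v 10% in 47%.

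**Step 3: the opposite error.** With identical true discontinuation rates d, the chance of a flag is 1 − P(no flag). By symmetry, half of the flags name 30 mg/m² as the safer dose.

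| d | Flag | Names 30 mg/m² safer |
|---|---|---|
| 10% | 17.8% | 8.9% |
| 20% | 31.3% | 15.7% |
| 30% | 37.9% | 18.9% |

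These figures take the discontinuation criterion alone.

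**The case against.** **The rule has two criteria.** Similarity needs silence on both, and independence may be the wrong assumption. The documents do not say whether a fatal reaction also counts as a discontinuation. If it does, and non-fatal discontinuations are 10% at both doses, 2% v 5% deaths ends in a similarity conclusion in about 57% of trials by simulation. If the dose with more deaths also has more non-fatal discontinuations (15% v 10%), a doubling from 2% to 4% does so in only about 32%. This stands. A reader might infer that a doubling or more of fatal reactions would usually be called similar. The documents give no base rate to support that, and from 5% v 10% upward it fails even on deaths alone.

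**The dose choice is protected in one direction.** If OS is similar, both a similarity conclusion and a finding against 30 mg/m² lead to 20 mg/m². If OS differs, the summary rule does not use safety. This also stands. A reader might infer that the rule could select 30 mg/m² by overlooking excess deaths there; it cannot do so by that route.

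**The chance reversal is limited.** It matters only when OS is judged similar, and it assumes equal true discontinuation rates. If 30 mg/m² is truly worse, the chance of naming it safer on this criterion is about 2% (10% v 13%) or 0.7% (10% v 15%).

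**The analysis is labelled exploratory, and section 9.5 tabulates safety by group.** Readers would therefore see the counts. But the section still instructs that similarity be concluded, and that wording goes beyond an exploratory reading.

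**Conclusion.** The point holds as a fault in what section 9.6 allows the trial to state. It converts a lack of flags into a conclusion of similar safety without any confidence bound, in a study that section 9.1.3 says is not comparative between doses. The clearest illustration needs no assumed rate: with 130 per dose, 2 v 8 drug-related deaths raises no flag, although differences up to about 10 points remain compatible with the data.

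How often a true doubling passes rests on assumed rates. It passes in most trials when fatal reactions are up to about 4% at the better dose, counting the death criterion alone, and less often under the full rule.

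Where OS is similar, the harm from a missed excess at 30 mg/m² is an unsupported safety statement, not a changed dose. The error that can change the dose is the chance flag on discontinuations, at 9 to 19% under equal true rates of 10 to 30%.

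**What to change.** In section 9.6 and the SAP:

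1. For each criterion separately, report the DT 30 minus DT 20 risk difference with its 95% CI.
2. Replace the sentence concluding similar safety with: no safety difference shown; differences up to [CI limit] not excluded.
3. Describe the final default to the lower dose as a tie-break and not as evidence of equal safety.

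This leaves the 5-point trigger in place. Removing it would leave the best-tolerance step without a working rule, because Fisher alone has only 7% power for 2% v 4% and 25% for 5% v 10%. When the trigger fires, the interval from item 1 shows the reader how firm the finding is.

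The cost is a wording change and two intervals, with no new data. The downside is that the trial gives up a claim of similar safety between doses.

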
Under the assumptions of a median survival of the control group of 8 months and a hazard ratio of 0.69, the required total sample size to achieve a 85% power to compare the experimental group (pooled DT 20mg/m² and DT 30mg/m² groups) versus BSC with a significance level of 2.5% one sided is 348 patients in the ITT population (116 patients in the BSC group and 232 patients in DT groups). It is expected that 10% of patients will be lost to follow-up; this leads to a calculated total sample size of 390 randomised patients.
 
Child Pugh A population (85% of the patient population):
 
Under the assumptions of a median survival of the control group of 9 months and a hazard ratio of 0.68, the required total sample size to achieve a 80% power to compare experimental group (pooled DT 20mg/m² and DT 30mg/m² groups) versus BSC with a significance level of 2.5% one sided is 291 patients in the ITT Child Pugh A population (97 patients in the BSC group and 194 patients in DT groups). It is expected that 10% of patients will be lost to follow-up; this requires for a calculated total sample size of 324 ITT Child Pugh A randomised patients.
 
Main efficacy analyses:
 
Results will be presented by treatment group and with all treatment groups pooled.
 
The primary endpoint is overall survival in the ITT population (all randomized patients). The 95% confidence intervals for hazard ratios and median times will be constructed and the Kaplan-Meier method will be used and plotted as curves by treatment group (pooled DT 20mg/m² and DT 30mg/m² groups) versus BSC group. The comparison between experimental group and BSC group will be made using the unstratified LogRank test. The analysis will be performed when 285 events have been observed.
 
The hierarchical sequential closed test procedure will be used to control the overall type I error rate of 5% to evaluate first the OS primary endpoint in the ITT overall population, then if statistically significant, the OS primary endpoint in ITT Child Pugh A population and then if statistically significant, the two main secondary endpoints (PFS and OOR) in the ITT Child Pugh A population.
 
To determine the optimal dose of DT between 20mg/m² or 30 mg/m², all statistical analyses (efficacy and safety) will be repeated as exploratory in the DT 20mg/m² group alone versus BSC and DT 30mg/m² group alone versus BSC. The dose of DT which presents the best benefit/risk ratio will be selected.
 
For secondary and exploratory endpoints, all time to event endpoints will be estimated using the Kaplan-Meier method and plotted as curves by treatment groups. The comparisons between DT groups and BSC will be made using LogRank tests. Proportion of subjects with objective response, disease control... will be compared between DT groups and BSC by the chi-square test. Estimates and 95% confidence intervals for the difference in proportions between DT groups and BSC will be provided. Estimate and confidence intervals for the odds-ratio will also be provided.
		

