9.4 Efficacy endpoints

9.4.1 Primary endpoint

The primary endpoint is overall survival (OS), defined as the time from the date of randomisation to the date of death from any cause. Patients without death at the time of the statistical analysis will be censored at the date they were last known to be alive.

The primary endpoint will be analyzed in ITT population (primary analysis), with an additional analysis in PP population.

Definition of date of death or censoring will refer to FDA guidelines for OS (definition including documented death only).

OS will be estimated using the Kaplan-Meier method and plotted as curves by treatment group.

The comparison between groups (pooled DT groups versus BSC) will be made using the unstratified LogRank test. The analysis will be performed when 285 events have been observed. The hierarchical sequential closed test procedure for a comparison of pooled DT groups with

BSC in the ITT Child Pugh A population will be used to control the overall type I error rate of 5%.

In addition to the analysis not adjusted for baseline characteristics considered above, a sensitivity analysis will be conducted using a Cox model adjusting for geographical region and pre-defined selected prognostic factors as recently described in this population such as ECOG score, BCLC stage, macroscopic vascular invasion, extrahepatic spread and hepatic impairment (Child Pugh score, prothrombine time) (Marrero J.A., 2013^[54], Reig M., 2013^[55], Iavarone M., 2015^[56]). HR, median and mean survival and OS rates every 3 months will be given with the corresponding 95% confidence intervals.

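### Section 9.6 calls the two doses 'similar' on OS from tests against BSC, not against each other; read consistently, that criterion is not met when DT beats BSC, and no gate stops an 'optimal' dose being named after a failed trial

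*Combined protocol and SAP*

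**What the plan says.** Finding the optimal DT dose is a secondary objective (section 2.2). The synopsis states the aim: "The dose of DT which presents the best benefit/risk ratio will be selected". Section 9.6 repeats it: "The selection of the optimal DT dose will be based on the benefit/risk ratio of each dose of DT".

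Section 9.6 then sets out an ordered rule:

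- **Efficacy.** A dose is identified on OS if one of the two exploratory log-rank tests against BSC is significant, or if a difference in favour of one dose reaches p below 15%.
- **'Similar' efficacy.** The doses count as similar when there is no difference, spelled out as "unstratified log-rank tests between the DT 30 mg/m² versus BSC or DT 20 mg/m² group versus BSC more than 15" per cent.
- **Safety.** The two doses are compared by Fisher tests on discontinuations and deaths due to adverse drug reactions, with an absolute difference of more than 5% as an alternative trigger.
- **Order.** Best OS decides first. Tolerance comes next: "If OS is similar between the 2 doses of DT, the optimal DT dose will be the one associated with the best tolerance". Last comes a default: "If OS and safety are found to be comparable between doses, then the lowest dose (20mg/m²) will be selected".

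Section 9.1.3 says the study is not comparative between the two doses. The primary test is a separate matter: "The comparison between groups (pooled DT groups versus BSC) will be made using the unstratified LogRank test" (section 9.4.1). Neither section 9.6 nor the synopsis makes dose selection depend on its result.

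**The concern.** The criterion for 'similar' answers a different question from the one asked. Whether each dose separates from BSC says little about whether the doses differ from each other. Two doses that both clearly beat BSC may be equally effective, yet they fail the stated criterion. Two doses with p = 0.16 and p = 0.90 against BSC would pass it.

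The tolerance step hangs on that criterion. If it is not met when DT works, the planned safety contrasts have no written role in the choice where the choice matters most, despite the benefit/risk aim. Conversely, if DT does not beat BSC, the rule can still run to its end and label a dose optimal.

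**Working it through.** **Inputs from the documents.** Patients are "randomised according to a 1:1:1 ratio to receive either DT 20 mg/m², DT 30 mg/m², or BSC" (section 3). Section 9.1.3 sets the level: "The type I (α) error will to be 5% (two-sided) for all analyses". Section 9.1.2 gives 285 deaths, a hazard ratio of 0.69, a control median of 8 months, 85% power and 390 patients (130 per arm).

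**The plan's own figure.** With pooled DT to BSC at 2:1, z = √(285 × 1/3 × 2/3) × |ln 0.69| − 1.96 = 7.958 × 0.3711 − 1.96 = 0.993. Power is 84.0%, close to the stated 85%.

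**Step 1: both p-values above 15%.** Suppose equal deaths d per arm. Each dose's log hazard ratio against BSC has variance 2/d. The pooled log hazard ratio is about the mean of the two, with variance 1/d + 1/(2d) = 3/(2d). Hence

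pooled z ≈ (z20 + z30)/√3.

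A two-sided p of 0.15 corresponds to |z| = 1.4395. If both p-values exceed 0.15, pooled |z| ≤ 2 × 1.4395/1.732 = 1.662, so pooled p ≥ 0.097. For unequal splits of the 285 deaths (BSC/DT 20/DT 30), the floor is 0.082 at 130/77.5/77.5 and 0.133 at 25/130/130. To be compatible with a significant pooled test, the cut-off would have to lie below about p = 0.09 at equal deaths (1.96 × √3/2 = 1.697, two-sided p = 0.0896).

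**Step 2: simulated log-rank tests.** There were 10,000 trials per scenario, 130 per arm, cut at the 285th death. Accrual over 56 months and exponential loss to follow-up are assumptions. Hazard ratios are for the two doses against BSC; 'positive' means a significant pooled benefit.

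| Hazard ratios | Positive | Of positive: both p < 0.15 | Exactly one | Neither |
|---|---|---|---|---|
| 1.0 / 1.0 | 2.8% | 64.6% | 35.4% | 0 of 280 |
| 0.69 / 0.69 | 85.4% | 91.4% | 8.6% | 0 of 8,539 |
| 0.80 / 0.80 | 44.4% | 79.9% | 20.1% | 0 of 4,437 |
| 0.80 / 0.60 | 85.2% | 64.3% | 35.7% | 0 of 8,517 |
| 1.0 / 0.69 | 33.0% | 20.4% | 79.6% | 0 of 3,301 |
| moderately non-proportional | 62.2% | 73.6% | 26.4% | 0 of 6,222 |

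In total, 0 of 31,296 positive trials had both p-values above 0.15. When both did exceed 0.15, the smallest pooled p was 0.080 at 0.69/0.69 and 0.062 in the non-proportional scenario.

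**Step 3: the literal 'or'.** Take p = 0.01 and p = 0.30, both in favour of DT: pooled z ≈ (2.576 + 1.036)/1.732 = 2.09, a positive trial. One test is significant, so an optimal dose is identified; one test is above 15%, so the doses are also 'similar'. This overlap is the 'exactly one' column: 8.6% of positive trials at 0.69/0.69 and 79.6% at 1.0/0.69.

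**Step 4: failed trials.** With no effect at either dose, 76.9% of failed trials have neither dose below 15% and go on to tolerance and then the default. A further 9.9% have at least one dose below 15% in favour of DT, so a dose can be named on OS. At 0.69/0.69, 29.3% of failed trials have neither dose below 15%, 63.2% have one and 7.5% have both.

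**Step 5: limits of the bound.** Five further scenarios with differently shaped hazards in the two dose arms gave 212 exceptions in 8,228 positive trials. All came from strongly and oppositely crossing hazards (1 of 1,347, 23 of 377 and 188 of 1,825); the other two scenarios gave none. The bound is not an identity.

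**The case against.** The strongest reply is that section 9.6 is ambiguous rather than closed to safety. Its efficacy rule speaks of one test, or one dose, and does not clearly cover both doses falling below 15%. The summary sentence on similar OS, taken on its own, would send two equally effective doses to the tolerance step. On that view safety could decide many positive trials. This stands as far as it goes: a reader might infer that safety can never affect the dose in a positive trial, and the text does not establish that. What it does establish is that the only written criterion for 'similar' does not lead there, and that the commonest positive case has no explicit rule.

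Three further points also stand. The Fisher contrasts between doses are planned without any condition on OS, so safety will be reported in every case; what is missing is its role in the decision. OS counts death from any cause (section 9.4.1), so fatal toxicity already enters the efficacy step. The by-dose analyses are labelled exploratory and affect neither the primary test nor the type I error. Putting OS ahead of tolerability is also a legitimate ordering.

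Two replies carry less weight. Section 9.1.1 leaves further detail to a separate SAP, but the cut-offs are already fixed in 9.6 and contradict each other there. The exploratory label does not remove the need for a workable rule, because the output is a selected dose under a stated secondary objective.

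**Conclusion.** The point holds as a defect in the decision rule, not in the primary analysis. Read as both p-values above 15%, and under approximately proportional hazards, the criterion for 'similar' OS is incompatible with a significant pooled OS test. Read with 'or', it contradicts the sentence before it in about 9% of positive trials at 0.69/0.69, and in more if the doses differ. In the remaining 91% or so at that hazard ratio, best survival is the only instruction, and between equally effective doses that is chance. The percentages depend on the simulated hazard ratios and accrual; the algebra depends on 1:1:1 allocation with a shared control.

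The missing gate is a matter of text: a dose can be called optimal after the primary test fails. A reader might go further and infer that every trial must end with a named dose. The documents do not support that, because the summary's proviso that there be a dose with best OS can be read in more than one way, especially if both doses look worse than BSC. Nor do they say that a dose named after a failed trial would be claimed as effective. No view is taken here on which dose is right.

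**What to change.** Change the wording of section 9.6 in two places and align section 9.1.3 and the synopsis.

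1. **Gate.** State that an optimal dose is declared only if pooled DT versus BSC is significant for OS in the ITT population; otherwise by-dose results are descriptive and no dose is selected.
2. **Definition of 'similar'.** Replace the 15%-against-BSC cut-off with a pre-specified exploratory between-dose criterion. For example, report the DT 30 versus DT 20 hazard ratio for OS with its confidence interval, and treat OS as not separating the doses unless the interval at a stated level excludes 1. Say that this covers the case of both doses below 15%, and that the planned contrasts on discontinuations and deaths due to adverse drug reactions are then used whenever OS does not separate the doses.

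Section 9.1.3 should then say that this between-dose OS comparison is exploratory, instead of ruling out any comparison between doses.

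**Cost.** No new data are needed, and the only added analysis is one hazard ratio from OS data already collected. No dose is labelled optimal if the primary test fails. The between-dose comparison has no planned power: with 285 deaths split equally, 95 per arm, the standard error of its log hazard ratio is √(2/95) = 0.145. A 95% interval would exclude 1 only for an observed hazard ratio below exp(−1.96 × 0.145) = 0.75 or above 1.33. The level should therefore be chosen deliberately, and failing to exclude 1 should be described as not separating the doses, not as showing them equal.
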